Screening measures. 1) *Demographics* such as age and gender, race, ethnicity, income, current occupation and usual occupation; 2) *Medical history and current health status* for current diagnoses, symptoms and past health problems; 3) *Medications Questionnaire* to rule out medications that affect the metabolism of targeted constituents; 4) *Prime MD* for depression and anxiety symptoms [71]; 5) *Michigan Alcohol Screening Test Short form (SMAST)* [73]; and 6) *Drug Abuse Screening Test (DAST)* [74]. For those who are tobacco users, we will administer a Tobacco Use History that assesses amount and frequency as well as duration of tobacco use [11]. The following measures comprise the *Biomarker modifier questionnaires* (measures of factors that may moderate biomarkers at each clinic visit): 1) *Dietary Intake* assesses consumption of cruciferous vegetables since the prior visit; 2) *Medications Questionnaire* to assess any changes in medications taken since last visit and to determine use of any drugs that may affect the Nrf2 pathway; 3); *Safety measures: Health Changes and Adverse Events Scale* to assess the nature, severity, duration, action taken, and outcome of any adverse events. *Vitals:* Blood pressure and heart rate will be measured.

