Measurements: For the comparison between the two treatment groups, we will consider measurements excluding the baseline observation. Measurements will be taken from each subject in the two supplementation sequences as seen in the following diagram:

Group 1: Period #1 (watercress; A1) – washout – Period #2 (placebo; B2)

Group 2: Period #1 (placebo; B1) – washout – Period #2 (watercress A2)

The letter is used to denote supplementation (A for watercress and B for placebo) and the number, 1 or 2, denotes the period. We will assume, in the formulation of statistical models, that the measurements A1, A2, B1, and B2 are “normally distributed” in log-scale. These letters can represent one of our outcome variables: urinary mercapturic acid levels of specific toxicants (e.g. benzene, acrolein, crotonaldehyde, propylene oxide, etc.) or for mercapturic acids generally, or DNA adducts of acrolein.

Main Outcome Variables: Our data analysis will be based on the following “outcome variables”:

$$X1 = B2 - A1; \text{ and } X2 = B1 - A2.$$

This subtraction will cancel the “within-sequence” effects of all subject-specific factors, leaving only two to be modeled and analyzed: the Treatment (or Supplementation) effect and the Period (or Order) effect. The measurements will result in two independent samples. Each will have the same sample size if there are no dropouts or missing data. Otherwise the number of subjects for each group of measurements (i.e., X1 and X2) will differ if there are dropouts and missing data.

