We would obtain values of X1 or X2, which is a log of "ratio" for each subject in each of the two groups with different supplementation order, it's (watercress/placebo) for group 1 and (placebo/watercress) for group 2. We'll then compute the averages of these log ratios, i.e \bar{x}_1 and \bar{x}_2 . We will do this calculation separately for the double null group ($\hat{\alpha}_{nn}$), and single null group ($\hat{\alpha}_{np}$). We will compare this average ratio with the average ratio of the double positive group ($\hat{\alpha}_{pp}$). With the double nulls being about 15% of the population, *GSTM1* single nulls (45%) and *GSTT1* single nulls (23%), we expect to see 60 double nulls, 180 *GSTM1* single nulls, 92 *GSTT1* single nulls, and 68 double positive individuals. If there is no influence of *GSTM1* or *GSTT1*, the effect of watercress supplementation would be the same between the double null and the double positive group or between the single null and the double positive group. We will test for the significance of the genotypic effect by using a two-sample t test.

PROTOCOL TITLE: Watercress in Detoxification of Environmental Toxicants and

Carcinogens

VERSION DATE: July 23, 2020

In order to estimate the power for that comparison, we need information on the variability of mercapturic acid levels within and between subjects. We will compute the variances of each of these genotypic groups separately and then obtain a pooled variance estimate to compute our pooled t test statistic. Based on our previous work, we used an intra-subject CV of 0.4 and an inter-subject CV of 0.6, which translates to a pooled standard deviation of 0.657. According to Table 3, the percentage difference between the Placebo and PEITC groups with the double null genotypes varied from 29.8% to 95.4%, whereas the percentage difference for the double positive genotypes varied from 4% to 7%. In general, we will have 80% power to detect a difference of 35% between the double null and double positive group and given the range of difference between these two groups in Table 3, we expect to have good power to study this interaction between watercress and *GSTM1* or *GSTT1* genotypes.

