Multivariate Regression Analysis: We will use multivariate regression analysis to supplement the t-test by pooling the data together and using each of the primary outcome variables as dependent variable, separately. In addition to the variables representing the supplementation, treatment order, and status of *GST (M1, T1)* genotypes, the list of independent variables will include socio-demographic characteristics such as gender, age, smoker vs non-smoker, baseline smoking level (cigarettes per day), and intake of dietary nutrients. We will fit a linear mixed-effect model where the dependency in the repeated measurements on each individual will be captured through a random effect. The status of *GST (M1, T1)* genotypes will be modeled as fixed-effects and we will test for the null hypothesis of no association between the genotypes and each outcome. Our primary parameter of interest will be the interaction between the treatment order (pre vs post) and the genotype groups (double null, *GSTM1* single null, *GSTT1* single null, and double positives). We will perform a t-test to assess the significance of the interaction parameter. The residual covariance structure should be selected among several candidates, i.e. autoregressive, compound symmetry, unstructured, etc., to estimate the fixed and random effects. We do not anticipate much missing data on the participants. In general, we will assume missingness at random (MAR) and the likelihood-based linear mixed effect model will provide consistent estimates of our parameters of interest in presence of MAR. The models will be assessed through their Akaike's Information Criterion and Bayesian's Information Criterion. The normality of the outcome variables will be assessed and in presence of non-normality, we will also implement Generalized Estimating Equations to study the impact of watercress and genotypes on each outcome variable. We will use the statistical software R packages nlm and gee to perform the above analysis. These packages will also provide the flexibility to fit non-linear mixed effect models to assess the impact of watercress and genotype groups.

PROTOCOL TITLE: Watercress in Detoxification of Environmental Toxicants and Carcinogens

VERSION DATE: July 23, 2020

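### The genotype comparison of the watercress effect is not randomised and not adjusted for ancestry, age or sex: the t test has no covariates, and main effects of fixed traits in the mixed model cancel from it

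*Combined protocol and SAP*

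**What the plan says.** Section 15.0 (Statistical Considerations) forms a placebo-versus-watercress difference of log values for each person. It says the subtraction removes the within-sequence "effects of all subject-specific factors, leaving only two to be modeled and analyzed", the two being treatment and period. These log ratios are averaged by genotype group, and the double-null and single-null groups are each compared with the double positives: "We will test for the significance of the genotypic effect by using a two-sample t test". No covariate enters that test. The comparison is then repeated within smokers and within non-smokers, and the plan concedes limited power for double nulls among smokers.

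The paragraph on multivariate regression supplements the t test with a linear mixed model that has a random effect per person. Besides supplementation, order and genotype, "the list of independent variables will include socio-demographic characteristics such as gender, age, smoker vs non-smoker, baseline smoking level (cigarettes per day", ending with "and intake of dietary nutrients". Two genotype tests are named. One is a main effect: "we will test for the null hypothesis of no association between the genotypes and each outcome". The other is the main target: "Our primary parameter of interest will be the interaction between the treatment order (pre vs post) and the genotype groups". No interaction between a covariate and supplementation is written down.

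Section 5.0 (Screening measures) collects "age and gender, race, ethnicity, income, current occupation and usual occupation". Section 15.0 uses race and ethnicity only in the descriptive summary of participants.

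**The concern.** The crossover protects the watercress-versus-placebo comparison, because each person is their own control and order is randomised. It does not protect the comparison of that effect between genotype groups. Any trait that is distributed differently across genotypes and also changes the response to watercress can produce or hide a genotype difference.

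The covariate list looks like protection against this. For the traits that are constant within a person it is not: the differencing that makes the crossover efficient also removes their main effects. What would confound the genotype contrast is their effect on the response, and that needs an interaction with supplementation.

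The sponsor's own material makes adjustment a reasonable expectation. The baseline genotype means in Table 2 (Section 2.0) were adjusted for age and gender. Section 2.0 also cites a watercress study in which the reduction in DNA damage was greater in smokers than in non-smokers. That is a different endpoint, but it is a response that varies with a listed covariate. The preliminary PEITC trial enrolled smokers only, whereas this one mixes about 300 non-smokers with about 100 smokers (Section 10.0). At stake is whether a difference in response by ancestry, sex or age could be read as an effect of *GSTM1* or *GSTT1*.

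**Working it through.** **Inputs from the documents.** Section 15.0: log-scale SD 0.657; intra- and inter-subject CVs 0.4 and 0.6; 80% power for a 35% difference; of 400 people, 60 double nulls (15%) and 68 double positives (17%). Section 10.0: 350 needed, 400 enrolled.

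**Assumed.** Two-sided 5% level (not stated); strength of effect modification; difference in trait share between genotypes; share R² of genotype explained by the covariates.

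**1. The plan's own power.** With 350 completers the groups are 0.15 × 350 = 52.5 and 0.17 × 350 = 59.5. SE = 0.657 × √(1/52.5 + 1/59.5) = 0.124. Reading 35% as a log difference of 0.35, 0.35/0.124 = 2.81 and power = Φ(2.81 − 1.96) = 0.803. The stated 80% is reproduced. (Read as ln 1.35 = 0.300, power is 0.674.)

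**2. Why main effects cancel.** For person *i* with genotype *g* and fixed trait *x*, let the log outcome under supplementation *s* (1 watercress, 0 placebo) be

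*y* = aᵢ + γxᵢ + period + (τ + δgᵢ + θxᵢ)s + error.

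Watercress minus placebo gives

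*d* = τ + δgᵢ + θxᵢ ± period difference + error.

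The main effect γ is gone, so including it cannot change the estimate of δ. The modification θ remains. If θ is left out, the expected estimate is δ + θ × (share of *x* in one genotype group − share in the other).

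**3. Numerical check.** One simulated crossover, 60 v 68, with no true genotype difference in response and a fixed trait that is unevenly spread over genotype and modifies response. Supplementation × genotype estimate (SE):

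| Terms added | Complete pairs | About 14% missing period 2 |
|---|---|---|
| None | 0.12662 (0.10622) | 0.14277 (0.11114) |
| Main effects of two fixed traits | 0.12662 (0.10622) | 0.14810 (0.11056) |
| The same plus a visit-varying diet term | 0.10565 (0.10507) | 0.12883 (0.10998) |
| Fixed traits × supplementation | 0.06725 (0.10737) | 0.11276 (0.11247) |

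The first two rows are identical in complete pairs and nearly so with missing periods. This shows the mechanism; a single data set says nothing about typical bias.

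For that, 2000 replicates of the log-ratio regression used 400 people, log SDs of 0.385 within and 0.555 between persons (the plan's CVs), an assumed ethnicity share of 35% in double nulls v 15% in others, and an assumed modification of 0.20 log units by ethnicity. The mean estimate was 0.036 unadjusted and −0.004 adjusted, against a true 0. The gap of 0.040 equals 0.20 × (0.35 − 0.15), as the formula predicts.

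**4. Size of the bias under assumptions.** Low: 0.1 × 0.10 = 0.01, ratio e^0.01 = 1.01. High: 0.3 × 0.30 = 0.09, ratio e^0.09 = 1.09. With 60 v 68, SE = 0.657 × √(1/60 + 1/68) = 0.116. The shift is then 0.09 to 0.77 SE, and a nominal 5% test rejects about 5.1% to 12.1% of the time. The far corner of a wider grid (share difference 40 points, modifier ratio 1.5) gives a ratio of 1.18 and 28.6%.

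For scale, the double-null v double-positive contrasts in Table 3 are 1.327/1.070 = 1.24 (3-HPMA), 1.298/0.960 = 1.35 (HMPMA) and 1.954/1.061 = 1.84 (SPMA).

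**5. Cost of adjusting.** The standardised difference of 2.81 is multiplied by √(1 − R²). Power goes from 0.803 to about 0.79 (R² = 0.04), 0.77 (0.09) and 0.73 (0.16).

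**6. Reach of the smoking strata.** Among 100 smokers one expects about 15 double nulls and 17 double positives. Among 300 non-smokers one expects about 45 and 51.

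**The case against.** Five points can be made for the plan.

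- **The covariate list is not confined to fixed traits.** It ends with dietary intake, and Section 5.0 has a questionnaire that "assesses consumption of cruciferous vegetables since the prior visit". A visit-varying term need not cancel, and in the check it moved the estimate. This stands, so a reader should not infer that every listed covariate is inert. But adjusting for diet does not remove confounding of genotype by a fixed trait.
- **Smoking status is already handled.** Within a smoking stratum it cannot confound genotype. This stands, and the inference that a smoker/non-smoker difference would go unnoticed as a genotype effect is not supported. The strata do nothing for age, sex or ancestry.
- **The plan never says main effects only.** The covariates are introduced as examples, and Section 15.0 also mentions undefined baseline parameters that differ by product. True, but an interaction that is not written down is not prespecified.
- **The covariates have a use.** They adjust the genotype main-effect test (in the check it moved from 0.048 to −0.099). And if the stated interaction with treatment order literally means sequence, it is a between-person contrast and the covariates do not cancel. Both stand. But on that reading the parameter is no longer the watercress-by-genotype effect, and the plan still has no adjusted estimate of it.
- **No confounder is shown.** The documents link neither *GSTM1* nor *GSTT1* status to ancestry, age, sex or smoking in this population. This stands: it limits what can be said about size and makes ancestry the main candidate, since it is inherited along with genotype.

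**Conclusion.** The point holds in this form. The genotype contrast in watercress effect is non-randomised and is tested without covariates. The mixed model prespecifies no covariate-by-supplementation term, so main effects of sex, age, smoking status and baseline cigarettes do not adjust that contrast: exactly so in complete pairs, almost so with some missing periods. Beyond the smoking-stratified analysis, nothing addresses fixed traits, and race and ethnicity are collected but unused in the model.

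The size rests wholly on assumed inputs: a spurious 1% to 9% for modification of 0.1 to 0.3 log units and share differences of 10 to 30 points. That is small against the Table 3 contrasts. A reader might go further and conclude that the planned genotype finding would be an artefact, or that the report will claim an adjustment it lacks. The documents support neither. This is a cheap improvement to the analysis, not a flaw that undoes the design.

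**What to change.** **t test paragraph of Section 15.0.** Supplement or replace the t test with a linear regression of each person's log ratio on genotype group plus race/ethnicity, smoking status, sex and age, with a sequence (period) term. Define the ratio as watercress over placebo in both sequences. At present both formulas subtract watercress from placebo, while the accompanying text gives the ratio opposite directions in the two groups.

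**Mixed-model paragraph of Section 15.0.** State the primary interaction as supplementation × genotype. Beside it, add supplementation × race/ethnicity first, then supplementation × smoking status, sex and age. Name race/ethnicity in the covariate list and fix its categories in advance.

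Amount smoked during follow-up should not serve as an adjustment variable, because it is measured after randomisation. If it is used at all, label it exploratory.

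**Cost.** SAP wording, a few more parameters, and the small loss of power shown above. These covariates are already collected at screening.

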Study design. Participants will be asked to attend clinic visits on days 0 (the day of product distribution), 4 (± 1 day), 7 (± 1 day) and 14 (± 1 day) for each of the periods they are receiving product and weekly during the 4 week washout between periods (see **Figure 2**). We use a 4-week washout period because the 1-week washout in our preliminary studies may not have been sufficient [11]. Each visit is composed of three parts and will be completed in a single day. Part 1: Prior to the clinic visit the participant will collect their first morning void urine. Part 2: In a virtual visit, participants will be asked to complete multiple online surveys (see **Table 4**). Part 3: Participants will drop off their first morning void urine (also used to test for pregnancy) at the research clinic (University of Minnesota – Tobacco Research Programs, [name]). Blood (once allowed), blood pressure, saliva, oral rinse, and buccal cells will be collected. After this collection, participants will be provided with either the watercress powder or the placebo and the flavoring product. Subjects will be given written instructions on how to add the watercress/placebo powder and flavor product to water and will also be provided a link to a video with instructions. They will be provided three different flavors from which they can sample. At the Day 4 visit, they will be asked to choose one of the flavors to be used during the rest of this phase. They will be asked to drink the formulation at breakfast, lunch and dinner. Participants will receive one jar of the FDWC on day 0 and the second jar on day 7. Participants will receive one jar of maltodextrin on day 0, which will last until the end of the study. A log will be kept of the products that are dispensed and any amounts unused. At the end of each two-week period (or end of study participation, whichever comes first), we will ask all participants to return any unused product. Compliance of use of the study products will be determined by the product accountability log and biochemical verification (e.g., urinary PEITC-NAC and total isothiocyanates). Participants will be provided standardized counseling about the importance of using the assigned products as directed and if procedural compliance is an issue, the research assistant will discuss the obstacles and develop a plan to overcome these obstacles. Participants will also be provided a urine collection cup, dietary intake log and dosing log at each visit.

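### The mixed model has no participant-by-period term, so choosing its covariance by AIC/BIC permits standard errors for treatment and treatment-by-genotype that are too small

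*Combined protocol and SAP*

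**What the plan says.** Section 15.0, Multivariate Regression Analysis, sets out a linear mixed model in which "the dependency in the repeated measurements on each individual will be captured through a random effect". A few sentences later it adds: "The residual covariance structure should be selected among several candidates, i.e. autoregressive, compound symmetry, unstructured, etc., to estimate the fixed and random effects". On choosing between fits it says: "The models will be assessed through their Akaike's Information Criterion and Bayesian's Information Criterion". It does not say which criterion decides if the two disagree, or whether the residual structure runs over all of a participant's visits or restarts in each period. No participant-by-period effect is named.

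The model's role is stated: "We will use multivariate regression analysis to supplement the t-test by pooling the data together". Within the model, "Our primary parameter of interest will be the interaction between the treatment order (pre vs post) and the genotype groups". A second route is conditional: "in presence of non-normality, we will also implement Generalized Estimating Equations".

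The t-test that the model supplements works on one between-period log difference per participant (X1 or X2, under Main Outcome Variables). Section 5.0 gives the visits: "Participants will be asked to attend clinic visits on days 0 (the day of product distribution), 4 (± 1 day), 7 (± 1 day) and 14". Section 15.0 lists day 2 instead of day 4. The two must be reconciled, but both give three post-baseline visits per period, and Section 15.0 leaves day 0 out of the treatment comparison.

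**The concern.** A participant takes one product throughout a period, and the periods are separated by a four-week washout. Visits inside one 14-day period can share things that differ from the other period, such as exposure, diet, smoking level and adherence. Treatment and treatment-by-genotype are therefore contrasts between participant-periods, and three visits in a period carry less information about them than three independent observations.

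A single participant effect absorbs only what is common to all six visits. Compound symmetry over all six visits has the same form as a random intercept, so it adds nothing. AR(1) picks up part of the within-period correlation. Unstructured residuals over all six visits capture it fully, but cost 21 covariance parameters, which BIC penalises heavily. The selection step may therefore settle on a form whose standard error is too small, and some genotype interactions would be declared at more than the nominal rate. Each outcome is modelled separately, so different mercapturic acids could end up with different structures and different error rates.

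**Working it through.** **The plan's own figure.** The 80% power in Section 15.0 belongs to the t-test. With 350 evaluable, 15% double null (52.5) and 100 − 15 − 45 − 23 = 17% double positive (59.5), SD 0.657, and 35% read as 0.35 log units, SE = 0.657 × √(1/52.5 + 1/59.5) = 0.124. Power = Φ(0.35/0.124 − 1.96) ≈ 80%, with two-sided alpha 0.05 assumed. It reproduces on that reading and does not depend on the mixed model.

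**Inputs for the check.** Intra-subject CV 0.4 (Section 15.0) gives log-scale within-person variance s² = ln(1 + 0.4²) = 0.148. There are two periods with three visits each. Let ρ be the share of s² common to the visits of one period. The documents do not give ρ; I use 0.10 to 0.50. I read the key interaction as treatment by genotype, although the plan words it as treatment order by genotype.

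**Random intercept alone (equivalently, with participant-level compound symmetry).** The true variance of a participant's period difference is (2/3)(1 + 2ρ)s². The pooled residual has 5 degrees of freedom per person, 4 within periods and 1 between: [4(1 − ρ) + (1 + 2ρ)]/5 = 1 − 0.4ρ. The model therefore reports (2/3)(1 − 0.4ρ)s², and

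SE ratio = √[(1 − 0.4ρ)/(1 + 2ρ)]; type I error = 2Φ(−1.96 × ratio).

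At ρ = 0.25 the ratio is √(0.9/1.5) = 0.775, and the error is 2Φ(−1.518) = 12.9%. For the double-null versus double-positive contrast (60 vs 68), the reported and correct SEs are 0.0546 and 0.0610 at ρ = 0.10, 0.0529 and 0.0682 at 0.25, and 0.0498 and 0.0788 at 0.50.

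**What the selection step would keep.** Each candidate covariance V was fitted to the true covariance Σ by expected normal likelihood. The excess deviance is n[ln|V| + tr(V⁻¹Σ) − ln|Σ| − 6]. AIC adds 2k and BIC adds k·ln n, with k = 2 for the random intercept (RI), 3 for RI plus AR(1) on visit order, and 21 for unstructured (UN). For n = 350:

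| ρ | Error, RI | Error, AR(1) | AIC: RI / AR(1) / UN | BIC: RI / AR(1) / UN | AIC keeps | BIC keeps |
|---|---|---|---|---|---|---|
| 0.10 | 8.0% | 6.8% | 16.3 / 13.5 / 42.0 | 24.0 / 25.1 / 123.0 | AR(1), 6.8% | RI, 8.0% |
| 0.20 | 11.2% | 8.6% | 52.7 / 34.3 / 42.0 | 60.4 / 45.9 / 123.0 | AR(1), 8.6% | AR(1), 8.6% |
| 0.25 | 12.9% | 9.5% | 80.5 / 49.4 / 42.0 | 88.2 / 61.0 / 123.0 | UN, 5.0% | AR(1), 9.5% |
| 0.30 | 14.6% | 10.4% | 115.1 / 67.7 / 42.0 | 122.9 / 79.2 / 123.0 | UN, 5.0% | AR(1), 10.4% |
| 0.50 | 21.5% | 14.6% | 341.3 / 180.1 / 42.0 | 349.0 / 191.6 / 123.0 | UN, 5.0% | UN, 5.0% |

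Between the last two rows, BIC holds AR(1) up to about ρ = 0.39 (121.0 against 123.0 for UN), where the error is 12.2%.

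A participant-by-period term (k = 3) scores AIC 6.0 and BIC 17.6 in every row. It beats all three candidates on both criteria, with SE ratio 1.000 and error 5.0%.

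**Other groupings.** AR(1) restarted in each period gives 6.0 to 7.8%. Compound symmetry within period gives 5.0%.

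**Smokers alone.** Take 25% of 350, about 88. At ρ = 0.25 both criteria keep AR(1), 9.5%. At ρ = 0.50 AIC keeps UN (42.0 against 49.8), 5.0%, while BIC keeps AR(1) (57.2 against 94.0), 14.6%. Section 15.0 announces the smoker analysis before it describes the regression, so fitting the mixed model there is an assumption.

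**The case against.** A reader might infer that the plan treats the three visits as independent and that its error rate is therefore the random-intercept column, from 8% up to 22%. The documents do not support this. "The residual covariance structure should be selected among several candidates" is in the same paragraph, independent residuals are not a named candidate, and the random effect is not said to be an intercept only. From ρ = 0.20 upwards both criteria discard the lone intercept, so the 11 to 22% figures describe a model that the plan's own step would reject. Unstructured residuals, or compound symmetry grouped within period, remove the problem altogether.

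A reader might also infer that the trial's main test is compromised. That is not supported either. The model supplements a t-test on X1 and X2, which is already a period-level analysis and carries the power statement. It is unaffected if each participant contributes one value per period, although Section 15.0 does not say how three visits become one value.

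Two further cautions stand. At ρ = 0 there is no inflation. The plan also mentions different baseline parameters for the two products in the regression; the check includes none, and their effect on the inflation is untested.

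What remains is that the candidates include forms that do not cure the problem, the criteria can disagree, and no rule settles which form is used. GEE is planned only for non-normal outcomes, so it is no general safeguard. Although the model is supplementary, the plan places its primary interaction parameter there.

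**Conclusion.** The point holds as a weakness in how the supplementary mixed model is specified: the plan permits, but does not commit to, a standard error that is too small. Under its selection rule, the type I error for treatment and treatment-by-genotype is about 5 to 10% over most of the assumed range of ρ for 350 participants, with a peak near 12% if BIC decides. It could reach about 15% if the model is fitted to smokers alone, BIC decides and ρ is 0.50.

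These figures rest on the assumed ρ, a within-period correlation that is constant across visits, complete data, two-sided 5% tests, and expected rather than sampled AIC and BIC. A single data set could select differently. The documents cannot fix the actual size. The change is still worth making, because the present rule is data-driven and a model with only three covariance parameters avoids the inflation at every ρ examined.

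**What to change.** State in Section 15.0 that the main mixed model for the treatment-by-genotype interaction has random effects for participant and for participant-by-period, and is the same for every outcome. A random intercept with compound symmetry within period is equivalent when the within-period correlation is positive. An analysis of period means is equivalent for balanced data.

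Keep unstructured and autoregressive residuals as sensitivity analyses, with their grouping stated. Drop only compound symmetry at participant level, since it duplicates the random intercept. Confine AIC and BIC to describing the sensitivity fits. Kenward-Roger degrees of freedom are optional at these group sizes.

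The cost is one sentence and a standard model option. Intervals will be wider than under the structure otherwise kept: about 12% wider than the random intercept at ρ = 0.10 (1/0.894 = 1.12), and about 17% wider than AR(1) at ρ = 0.25 (1/0.852 = 1.17). That width is the correct one.
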